10.1.2 Analysis Sets

The analysis of all endpoints, unless noted otherwise, will be conducted on the Safety Analysis Set defined as all subjects that are enrolled and receive at least 1 dose of AMG 224. The analysis of DLT will be restricted to DLT-evaluable subjects (see [Section 3.4](#)). The PK Analysis Set will contain all subjects who have received at least 1 dose of the investigational product and have at least 1 PK sample collected. These subjects will be evaluated for PK analysis unless the number of data points required for analysis is not enough, or significant protocol deviations have affected the data, or if key dosing or sampling information is missing.

10.1.3 Covariates and Subgroups

The relationship of covariates to efficacy endpoints will be explored if appropriate. Biomarker data may be incorporated in additional exploratory subgroup or multivariate analyses. The analyses of biomarkers may be performed after collection of all samples during the conduct of the study and therefore may be reported after the primary analysis of efficacy endpoints.

10.2 Sample Size Considerations

It is anticipated that approximately 60 subjects will be enrolled in this study. Approximately 40 subjects will be enrolled in the dose exploration cohorts and up to 20 additional subjects will be enrolled in the dose expansion cohort. The sample size in the dose exploration is based on practical consideration and it is consistent with conventional oncology studies with the objective to identify the MTD. With 3 subjects per cohort, there is a 27 to 70% probability of observing at least one DLT if the true DLT rate is 10 to 33% and with 6 subjects per cohort, there is a 47 to 91% probability.

In the dose expansion cohort, a subject number of 20 (regardless of group) will provide a 64% probability of observing at least one adverse event with 5% incidence rate and 88% probability of observing at least one adverse event with 10% incidence rate. An exact 80% binomial confidence interval (CI) will be provided for overall response rate (ORR). With the 20 subjects and 20% ORR, the 80% CI would be 9% to 36%.

10.3 Planned Analyses

The following data analyses are planned: (1) dose decision analyses in the dose-exploration cohorts, (2) the primary analysis when target enrollment is complete 6 months on study or withdraws from the study, and (3) the final analysis after all subjects have ended the study.

10.3.1 Interim Analyses

Safety data will be reviewed on an ongoing basis. The Dose Level Review Team (DLRT, see [Section 10.3.2](#)) will review all available cumulative data by cohort prior to making dose escalation decisions. Adverse events and DLTs observed in all subjects will be evaluated continually and considered in all enrollment and dosing decisions.

During dose-expansion, the DLRT will review safety after 5 subjects have enrolled (combining Group A and Group B subjects) and completed 28 days on study. A TPI Bayesian model (see [Section 10.4.2.3](#)) utilizing all current DLT-evaluable subjects will be

Approved

fit to evaluate the appropriateness of the preliminary MTD from dose exploration. The subsequent subjects to be enrolled in dose expansion may be dosed with the updated dose level, determined by the DLRT.

10.3.2 Data Monitoring Committee (DMC), Data Review Team (DRT) or Dose Level Review Team (DLRT)

Dose Level Review Meetings (DLRMs) will be held to review data, monitor safety, and make decisions on dose escalation / change. The DLRT will be composed of the investigators or designees, and the following Amgen representatives: medical monitor, global safety officer or designee, clinical study manager, biostatistician, additional members may be added as needed (eg, clinical pharmacologist). The following members are responsible for DLRT decisions: investigators, Amgen medical monitor, and global safety officer or designee. All available study data, including data collected after the initial DLT window, and including demographics, IP administration, medical history, concomitant medications, adverse events, ECGs, vital signs, laboratory data, and PK/PD information will be reviewed. In addition to DLTs, all \geq grade 3 toxicities not meeting DLT criteria will be reviewed and may be considered in DLRT decisions. Modeling of available potential safety risk data (eg, for thrombocytopenia) to predict safety risk for dose escalation decisions may also be considered.

10.3.3 Primary Analysis

The primary analysis will occur when target enrollment is complete and each subject either completes 6 months on study or withdraws from the study.

10.3.4 Final Analysis

A final analysis is planned after all dose-exploration cohorts and dose-expansion subjects have ended the study.

10.4 Planned Methods of Analysis

10.4.1 General Considerations

Descriptive statistics will be provided for selected demographics, safety, PK, PD and biomarker data by dose, dose schedule, and time as appropriate. Descriptive statistics on continuous data will include means, medians, standard deviations and ranges, while categorical data will be summarized using frequency counts and percentages. Graphical summaries of the data may also be presented.

Approved

10.4.2 Primary Endpoints

10.4.2.1 Safety Endpoints

Unless otherwise specified, statistical analyses on safety endpoints will be done using subjects from the Safety Analysis Set, which includes subjects that are enrolled and received at least 1 dose of AMG 224.

10.4.2.2 Adverse Events

Subject incidence of all treatment emergent adverse events will be tabulated by system organ class and preferred term. The number and percentage of subjects reporting adverse events will be evaluated overall and by dose level and will also be tabulated by relationship to study drug.

Tables of fatal adverse events, serious adverse events, adverse events leading to withdrawal from investigational product, and significant treatment emergent adverse events will also be provided.

10.4.2.3 Dose Limiting Toxicities

The analysis of the probability of dose limiting toxicities (DLT) will include data from DLT-evaluable subjects, both from dose-exploration and dose-expansion (see [section 3.4](#) for definition of DLT-evaluable). The primary analysis will only include DLTs that occur within the protocol defined DLT evaluation interval. If DLTs occur outside the specified evaluation interval, a sensitivity analysis will be performed where DLTs occurring outside of the specified time interval are included. The preliminary estimate of the MTD will be identified using the 3+3 design. A final estimate of the MTD will be made based on a toxicity probability interval (TPI) Bayesian model utilizing all DLT evaluable subjects from the dose exploration and dose expansion cohorts ([Babb, 1998](#)). A minimally informative prior distribution will be used for the model parameters ([Neuenschwander, 2008](#)). The MTD target probability interval is (0.20, 0.35) and TPIs of (0.35, 0.60) and (0.60, 1.00) are defined as excessive and unacceptable, respectively. The model's predicted MTD is the dose with the highest probability of the target TPI, but with a less than 0.25 probability of an excessive or unacceptable TPI.

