- If a subject permanently ended the study treatment before completion of DLT evaluation period for a reason other than experiencing a DLT, then another subject will be recruited to replace this subject for the evaluation of the MTD.

Dose escalation will occur at the planned dose levels until the MTD is determined or until the highest dose level is tested. The MTD is defined as the highest dose level with an observed incidence of DLT in $< 33\%$ of subjects enrolled in a cohort dose level. At least 6 subjects will be treated at the MTD or highest tested dose.

A DLT will be defined as any of the events described under ([Section 6.2.1.6](#)), occurring in a subject during the DLT window, and regarded by the investigators and/or Amgen medical monitor to be related to AMG 224. The DLT window will be the initial 28 days of treatment with AMG 224. The DLT window may also be extended to assess events starting within the window in case the DLT definition is time dependent (neutropenia or thrombocytopenia, see below). Any adverse event occurring outside the DLT window that is determined by the investigator to be possibly related to the investigational product, which is seen more frequently or is more severe than expected or is persistent despite appropriate management, can be determined to be a DLT upon unanimous decision by the DLRT after review of the adverse event and all available safety data. The CTCAE version 4.0 will be used to assess the severity of toxicities/adverse events. The DLRT may request additional reviews or recommend modifying or suspending the study if safety concerns arise during the study. In the event that a need to modify or suspend the study is identified, this information will be communicated to investigators immediately, in accordance with Amgen procedures, and in compliance with prevailing guidance, including EMEA/CHMP/SWP/28367/07 (Guideline on strategies to identify and mitigate risks for first-in-human clinical trials with investigational medicinal products). Refer to [Section 10.3.2](#) for additional details regarding the DLRT.

Dose Exploration Stopping Rules

The DLRT may consider part 1 dose exploration complete if one of the following rules is met:

- The highest planned dose level is evaluated, MTD has not been defined and no DLTs occur at any dose level, in this case the maximum administrated dose (MAD) may be used for part 2.
- A total of 40 DLT-evaluable subjects have been enrolled.
- An MTD is identified.

Approved

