10.4.4 Secondary Endpoint(s)

10.4.4.1 Efficacy Endpoint Analyses

Listings will be produced for all subjects in the dose-exploration cohorts and the dose-expansion cohorts indicating the time to progression, time to response, and duration of response. The proportion of subjects with a partial response to treatment or better per the IMWG with corresponding exact 80% CI will be calculated using the Clopper-Pearson method (Clopper and Pearson, 1934) and tabulated for subjects treated at the MTD. The proportion of subjects with minimal residual disease and the proportion of subjects' progression-free at 6 months with corresponding exact 80% CI will be calculated using the Clopper-Pearson method. Kaplan Meier curve will be presented for time to progression and duration of response with estimates for rates and 80% CI at selected weeks.

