The dose exploration part of study is aimed at determining preliminary maximum tolerated dose (MTD). The preliminary MTD is defined as the maximum dose at which fewer than one third (< 33%) of subjects enrolled in a cohort dose level experience a DLT. A final estimate of the MTD will be made based on a toxicity probability interval (TPI) Bayesian model utilizing all DLT-evaluable subjects from the dose exploration and dose expansion cohorts. Based on the TPI model, the MTD is defined as the dose with the highest probability of a DLT rate between (0.20 and 0.35) while controlling the probability of excessive and unacceptable toxicity.

Minimal Residual Disease (MRD) Negativity

Tumor load of 10^{-5} target cutoff level is considered for the definition of MRD negativity ie, less than 1 clonal cell in 10^5 normal cells is defined as MRD negative.

(Paiva B, 2015)

Objective Response

Objective response is defined as a tumor response assessment of either stringent complete response, complete response, very good partial response or partial response per the International Myeloma Working Group Uniform Response Criteria for Multiple Myeloma (IMWG-URC) and will be determined only for subjects with measurable disease at baseline as per IMWG-URC for Multiple Myeloma.

Objective response will be determined based on the responses collected using Best Overall Response/Progression CRF.

Objective Response Rate (ORR)

Incidence of either PR or better (sCR, CR, VGPR) while on study as defined by the IMWG-URC. All subjects that do not meet the criteria for objective response by the analysis cutoff date will be considered non-responders.

Percent Change From Baseline

Percent change from Baseline is the arithmetic difference between post-Baseline and Baseline divided by Baseline values times 100.

Study Day

Post study day: study day= (date - date of Study Day 1) + 1

Pre study day: study day= (date – date of Study Day 1)

Study Day 1

Study day 1 is defined as the first day of administration of the investigational product after enrollment. The day prior to Study Day 1 is considered Day -1.

Serious TEAE

Serious adverse events (SAEs) are events categorized as AEs that are starting on or after first dose of investigational product as determined by the flag indicating if the adverse event started prior to the first dose on the Events CRF and up to and including 37 days after the end of investigational product.

Time to Response (TTR)

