9.6.1.2 Dose Limiting Toxicities

The analysis of the probability of DLT will be based on the DLT Evaluable Analysis Set. A listing and summary of the subject incidence of DLT will be provided.

A final estimate of the MTD will be estimated from the TPI Bayesian model utilizing all DLT-evaluable subjects. A sensitivity analysis may also be performed where DLTs

occurring outside of the specified time interval are included. A listing of DLTs occurring outside of the specified time interval will be produced to aid in determining if the sensitivity analysis should be conducted.

The planned doses for dose exploration cohort are 30, [REDACTED] of AMG 224. It will use a standard 3+3 design to guide dose escalation decisions and to make a preliminary estimate of the MTD. Dose level decision rules are specified in [Table 1](#).

In the dose expansion cohort, up to 20 subjects would be treated at the preliminary MTD. After 5 subjects (combining Group A and B) have completed 28 days on study, there will be a safety review by the DLRT. A TPI Bayesian model utilizing all current DLT evaluable subjects will be fit to evaluate appropriateness of preliminary MTD from dose exploration phase. As more subjects are treated, there may be a higher than expected incidence of DLTs or a higher than expected tolerance of treatment. If these scenarios (either with higher toxicity or tolerance) occur during expansion cohort the additional data will be used to refine the estimate of MTD established during the dose escalation phase. (Iasonos A and O'Quigley J, 2013).

A minimally informative prior distribution will be used for the model parameters (Neuenschwander, 2008). The MTD target probability interval is (0.20, 0.35) and TPIs of (0.35, 0.60) and (0.60, 1.00) are defined as excessive and unacceptable, respectively. The model's predicted MTD dose is the dose with the highest probability of the target TPI, but with a less than 0.25 probability of an excessive or unacceptable TPI.

The TPI design seeks to identify a dose most likely to have a DLT rate in the target TPI, but with overdose control that limits the possibility that the dose has an excessive or unacceptable DLT rate ([Babb et al, 1998](#)). The probability of a DLT at dose level d_i is assumed to follow a Bernoulli distribution with probability p_i where the logit of p_i increases linearly with the log of the standardized dose in the following 2-parameter logistic model:

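### The final-MTD rule has no 'MTD not reached' outcome: with no or few DLTs it labels the top tested dose the MTD, although the model places that dose mostly below the target DLT range.

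*Protocol*

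**What the plan says.** Protocol 10.4.2.3 sets a target DLT-rate interval of 0.20 to 0.35 and calls 0.35 to 0.60 excessive and 0.60 to 1.00 unacceptable. Under the model, the "predicted MTD is the dose with the highest probability of the target TPI". The single restriction is an overdose limit: at that dose, the two upper intervals together must carry a posterior probability under 0.25. SAP 9.6.1.2 repeats this ("predicted MTD dose is the dose with the highest probability of the target TPI"). SAP section 5 (Definitions) gives the same rule for the final MTD. SAP Appendix A describes an acceptable final dose by its rank on target probability (first or second) and the same 0.25 limit. None of these places sets a minimum target probability, a condition on P(DLT rate < 0.20), or an outcome in which no MTD is named.

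Elsewhere the plan accepts that an MTD may not be found. The primary objective is qualified as *if possible*. Protocol 3.3 refers to the MTD or the highest dose tested. Protocol 6.2.1.2 covers a Part 1 that reaches the highest planned dose with no MTD and no DLT at any level: "in this case the maximum administrated dose (MAD) may be used for part 2". Response is then "tabulated for subjects treated at the MTD" (protocol 10.4.4.1).

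**The concern.** The rule ranks doses by target probability and guards against one error only, excess toxicity. If every dose is probably below 0.20, target probability rises with dose, so the maximum falls on the top dose by construction. A target probability of 0.001 wins if all the others are smaller. The Part 1 provision does not help: it governs which dose may enter Part 2, it no longer applies after a single DLT, and the final model step follows it and can give the same dose the MTD label.

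Determining the MTD is a primary objective. An MTD tells the reader that a tolerability limit was located. Here the label could go to a dose for which the study's own model says the limit was not reached, and the response table tied to the MTD would carry that label too.

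**Working it through.** **Inputs.** SAP 9.6.1.2 and Appendix A: logit(p_i) = log α + β·log(d_i/d_max), with (log α, log β) bivariate normal, means 0.0536 and −0.1469, SDs 1.685 and 1.001, correlation −0.216. Protocol 3.1: at least 6 subjects at the MTD or highest tested dose. Protocol 3.3: up to 20 in expansion, so up to 26 at one dose. Protocol 6.2.1.1 and Table 2: 30 to 300 mg, eight cohorts.

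**Assumed, because redacted.** The dose levels and d_max. The worked grid is 30, 60, 90, 120, 150, 190, 250 and 300 mg with d_max = 300. Other eight-level grids with d_max 250 to 300 and a six-level grid ending at 250 were also run. Expansion subjects, who are dosed by weight, are placed at a single nominal level.

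**The plan's own figures first.** At d_max the log-dose term is zero, so P(p ≤ 0.20) = Φ((logit 0.20 − 0.0536)/1.685) = Φ((−1.386 − 0.0536)/1.685) = Φ(−0.854) = 0.196, against the stated 0.21. The prior median at 105 mg is 0.246 (d_max 300) to 0.281 (d_max 250), against about 0.275. At 30 mg, P(p ≤ 0.60) is 0.85 to 0.86, against 0.90. The SAP fits the prior to many quantiles by least squares, so 0.90 may be a target rather than an achieved value.

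**Posterior.** Numerical integration on an 801 × 801 grid of (log α, log β), then the rule of 10.4.2.3. Worked grid, 0/3 DLTs at each of the seven lower levels:

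| DLTs/n at top dose | P(<0.20) | P(0.20–0.35) | P(>0.35) | P(target), next dose down |
|---|---|---|---|---|
| 0/6 | 0.941 | 0.053 | 0.005 | 0.013 |
| 1/6 | 0.768 | 0.193 | 0.039 | 0.066 |
| 0/11 | 0.981 | 0.019 | 0.001 | 0.003 |
| 0/26 | 0.9993 | 0.0007 | <0.0001 | 0.0001 |
| 2/26 | 0.976 | 0.024 | 0.0001 | 0.003 |
| 3/26 | 0.927 | 0.072 | 0.001 | 0.010 |
| 4/26 | 0.831 | 0.166 | 0.003 | 0.028 |
| 6/26 | 0.509 | 0.457 | 0.034 | 0.119 |
| 7/26 | 0.337 | 0.583 | 0.080 | 0.193 |

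The top dose is named in every row. The label is plausible in the last row and not in the 0/6, 0/11 or 0/26 to 3/26 rows.

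**Other grids.** 0/6 gives P(<0.20) of 0.92 to 0.95, 0/26 gives at least 0.999, and 2 or 3 in 26 gives about 0.92 to 0.98. The top dose is always named.

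**Expansion below the top dose.** With 0/26 at the seventh level and 1/6 at the top, the worked grid gives P(<0.20) = 0.94. A scan of placements of 1 to 3 DLTs (at most one per lower dose) with expansion at the sixth or seventh level still selects the top dose every time. P(<0.20) is usually above 0.94 (the medians) but falls to about 0.67 to 0.90 when DLTs lie at or near a top dose with 6 subjects.

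**The opposite gap.** With 3/6 at 30 mg and no other data, P(>0.35) is 0.70 at 30 mg and higher at every dose above. No dose is eligible, and the plan does not say what is then reported.

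**The case against.** The strongest reply is that nothing is hidden. SAP 9.6.1.2 summarises the probability of each toxicity interval by dose, and P(<0.20) is one minus the sum of the three. SAP 9.5.2.1 gives best response by dose, and preliminary, final and combined rates if the two MTDs differ. A careful reader could see that the limit was not reached and find response at any dose. That stands, and it confines the point to the label. It does not correct the label, because no rule acts on the below-target probability.

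Second, the 3+3 stage defines the MTD as the highest level with observed DLT incidence under 33%, and 0/6 or 2/26 meets that. But the same text distinguishes the MTD from the highest tested dose, and the final estimate comes from the model with its own target interval.

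Third, the low-toxicity case may not arise. Amendment 2's rationale records no DLT and no MTD through Cohort 6, but the current text speaks of a preliminary MTD, and Amendment 4's rationale reports grade 4 thrombocytopenia above a redacted dose. Expansion may therefore be below the top level. The documents do not settle this, so I attach no frequency to the problem.

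A reader might infer three stronger claims. One is that the top dose is almost surely below target whenever DLTs are few; the 1/6 row (0.77) and the lower-dose expansion cases show otherwise. Another is that the rule always yields an MTD; it yields none if every dose fails the overdose limit. The third is that subjects would be dosed wrongly. The final estimate is a reporting step, and dose decisions rest with the dose level review team.

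**Conclusion.** The point holds for the final model-based rule. With no DLTs, or with 1 to 3 DLTs and expansion at the top dose, the rule names the top dose the MTD while the model gives a probability of about 0.92 or more that its DLT rate is below 0.20. The exception is a lone DLT among only 6 subjects there, at 0.77 on the worked grid. With expansion at a lower dose the mismatch remains but can be milder, down to about 0.67. The figures rest on assumed dose levels and d_max, a single nominal level for expansion, and the SAP's published prior. They change little across the grids tried. This is a labelling error on a primary objective and should be corrected before the final analysis. It is not a safety defect, and the interval probabilities needed to detect it are already planned.

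**What to change.** Add to protocol 10.4.2.3 and SAP 5 and 9.6.1.2:

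- If the selected dose is the highest dose tested and its posterior P(DLT rate < 0.20) exceeds a pre-specified cut, report *MTD not reached* and label the dose the maximum administered dose.
- State what is reported if no dose passes the overdose limit.
- Print P(<0.20) beside the other interval probabilities.
- When no MTD is reached, tabulate response at the maximum administered dose or RP2D.

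The sponsor should choose the cut and justify it. It should not be presented as a mirror of the 0.25 overdose limit. On the worked grid with 26 at the top, a cut of 0.90 gives *not reached* for 0 to 3 DLTs, 0.75 for 0 to 4, and *P(<0.20) exceeds P(target)* for 0 to 6. If the true top-dose rate were 5% or 10%, 3 or fewer DLTs in 26 would occur with probability 0.96 or 0.74. If it were 25%, inside the target, the binomial probabilities of at most 3, 4 and 6 in 26 are 0.08, 0.18 and 0.51. The last cut would therefore often deny an MTD that had been found. With 0.75, the 1/6 case (0.768) is close to the line.

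The cost is a few sentences and one output column, with no new data and no change to dosing. The downside is that the study may have to report that no MTD was reached.
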